## 14.3. Archiving

The investigator will keep all information relevant to the study for at least 25 years after the end of the study, or more if specified by the local regulation.

At the end of the study, the investigator or an authorized member of his/her team will download an electronic copy of each participant's data from the e-CRF and should keep it in a reliable, secure and durable location. The file includes all data and comments reported in the e-CRF, the history of all queries and signatures and the full audit trail reports.

The file must include appropriate restrictions (password protection) and adequate protection from loss, physical damage or deterioration for the duration of the archiving period.

#### 15. INSURANCE

I.R.I.S., or any parent company of SERVIER GROUP in charge of the management of clinical trials, is insured under the liability insurance program subscribed by LES LABORATOIRES SERVIER to cover its liability as sponsor of clinical trials on a worldwide basis.

Where an indemnification system and/or a mandatory policy are in place, I.R.I.S. or any parent company of SERVIER GROUP will be insured under a local and specific policy in strict accordance with any applicable law.

All relevant insurance documentation is included in the file submitted to any authorities' approval of which is required.

# 16. OWNERSHIP OF THE RESULTS – DATA SHARING POLICY AND PUBLICATION POLICY

I.R.I.S., acting as the study sponsor, assumes full responsibilities relating to this function and retains exclusive property rights over the results of the study, which it may use as it deems fit.

I.R.I.S. will ensure that the key design elements of this protocol will be posted in a publicly accessible database such as clinicaltrials.gov. In addition, upon study completion and finalization of the study report, the results of this study will be either submitted for publication and/or posted in a publicly accessible database of clinical study results.

Any project of publication and/or communication relative to the study and/or relative to the obtained results during the study or after the study end shall be submitted to the sponsor in accordance with the guidelines set forth in the applicable publication policy or financial agreement.

The investigator, who submitted the project, shall take the sponsor's comments into due consideration.

As the study is a multicentre one, the first publication must be performed only with data collected from several centres and analysed under the responsibility of I.R.I.S. The investigator commits himself not to publishing or communicating data collected in only one

centre or part of the centres before the publication of the complete results of the study, unless prior written agreement from the other investigators and I.R.I.S. has been provided.

Data Sharing Policy is available at https://clinicaltrials.servier.com/data-request-portal/. Researchers can ask for a study protocol, patient-level and/or study-level clinical trial data including clinical study reports (CSRs).

They can ask for all interventional clinical studies:

- submitted for new medicines and new indications approved after 1 January 2014 in the European Economic Area (EEA) or the United States (US).
- Where Servier or an affiliate are the Marketing Authorization Holders (MAH). The date of the first Marketing Authorization of the new medicine (or the new indication) in one of the EEA Member States will be considered within this scope.

In addition, Servier's data sharing policy includes all interventional clinical studies in patients:

- sponsored by Servier,
- with a first patient enrolled as of 1 January 2004 onwards,

for New Chemical Entity or New Biological Entity (new pharmaceutical form excluded) for which development has been terminated before any Marketing authorization (MA) approval

The datasets generated and/or analysed during the current study will be available upon request from www.clinicaltrials.servier.com after the Marketing Authorisation has been granted.

Summary results and a lay summary will be published on www.clinicaltrials.servier.com within 6 months after the end of the study.

#### 17. ADMINISTRATIVE CLAUSES

## 17.1. Concerning the sponsor and the investigator

#### 17.1.1. Persons to inform

In accordance with local regulations, the investigator and/or the sponsor will inform, the Director of the medical institution, the pharmacist involved in the study and the Director of the analysis laboratory.

# 17.1.2. Substantial protocol amendment and amended protocol

If the protocol must be altered after it has been signed, the modification or substantial amendment must be discussed and approved by the coordinator and the sponsor.

The substantial protocol amendment must be drafted in accordance with the sponsor standard operating procedure and an amended protocol must be signed by both parties. Both documents must be kept with the initial protocol.

All substantial amendments and corresponding amended protocols must be sent by the investigator(s) or the coordinator(s) or the sponsor, in accordance with local regulations, to

the IEC that examined the initial protocol. They can only be implemented after a favourable opinion of the IEC has been obtained, local regulatory requirements have been complied with, and the amended protocol has been signed, except for a measure required to eliminate an immediate risk to the study participants.

When the submission is performed by the investigator or the coordinator, the latter must transmit a copy of IEC's new written opinion to the sponsor, immediately upon receipt.

Furthermore, the substantial amendment and amended protocol are to be submitted to the Competent Authorities in accordance with local regulations.

# 17.1.3. Final study report

The study report will be drafted by Medical Writing Department in compliance with I.R.I.S. standard operating procedure.

The sponsor's representative and the coordinator must mutually agree on the final version. One copy of the final report must be dated and signed by the coordinator and the Director of the Center for Therapeutic Innovation.

The clinical study report, the summary of the results of the clinical trial together with a summary that is understandable to a layperson will be submitted where applicable within 6 months after the end of the clinical trial.

# 17.2. Concerning the sponsor

The sponsor undertakes to:

- supply the investigator with adequate and sufficient information concerning the IMPs and the NIMPs administered during the study to enable him/her to carry out the study,
- supply the investigator with investigator's brochure if the IMP is not marketed,
- obtain any authorisation to perform the study and/or import licence for the IMPs administered that may be required by the local authorities before the beginning of the study,
- provide the coordinator annually, or with another frequency defined by the local regulations, with a document describing study progress which is to be sent to the IEC(s).
- take all the necessary precautions to maintain the safety of the processed data, in particular their confidentiality, their integrity and their availability, by assessing risks identified concerning personal data protection. The following measures will be implemented (non exhaustive):
  - Management of authorisation to access to personal data (e-CRF)
  - Identification and authentication measures before accessing personal data (e-CRF)
  - o Traceability measures for the access to and modification of personal data (e-CRF)
  - Secured data transfer
  - o Time limit for storing personal data
- handle any security breach by implementing an internal committee (including CISO, DPO, communication department...) in order to qualify the security incident (Information systems, nature and number of personal data impacted), to define an action plan for corrective actions and to notify to relevant person (authority and/or if needed individuals).

## 17.3. Concerning the investigator

## 17.3.1. Confidentiality - Use of information

All documents and information given to the investigator by the sponsor with respect to S95014 and study CL2-95014-002 are strictly confidential.

The investigator expressly agrees that data on his/her professional and clinical experience is collected by the sponsor on paper and computer and stored for its sole use relating to its activities as the sponsor of clinical trials, in accordance with GCP.

He/she has a right to access, modify, and delete his/her own personal data by applying to the sponsor.

In case patient wants to exercise his/her rights regarding personal data protection, he/she will contact the investigator. The investigator will forward the request to the sponsor (see Appendix 7).

The investigator agrees that he/she and the members of his/her team will use the information only in the framework of this study, for carrying out the protocol. This agreement is binding as long as the confidential information has not been disclosed to the public by the sponsor. The clinical study protocol given to the investigator may be used by him/her or his/her colleagues to obtain the informed consent of study participants. The clinical study protocol as well as any information extracted from it must not be disclosed to other parties without the written authorisation of the sponsor.

The investigator must not disclose any information without the prior written consent from I.R.I.S., except to the representatives of the Competent Authorities, and only at their request. In the latter case, the investigator commits himself/herself to informing I.R.I.S. prior to disclosure of information to these authorities.

A participant screening log and a full identification and enrolment list of each participant will be completed and kept in a safe place by the investigator who should agree to provide access on site to the auditor and/or the representatives of the Competent Authorities. The information will be treated in compliance with professional secrecy.

The participant screening log must be completed from the moment the investigator checks that a participant could potentially take part in the study (by assessment of participant medical history during a visit or by examination of the medical file).

#### 17.3.2. Organisation of the centre

Every person to whom the investigator delegates under his/her responsibility a part of the follow-up of the study (co-investigator, nurse...) and any other person involved in the study for this centre (cardiologist, pharmacist...) must figure in the "Organisation of centre" document.

This document should be filled in at the beginning of the study and updated at any change of a person involved in the study in the centre.

#### 17.3.3. Documentation supplied to the sponsor

The investigator undertakes before the study begins:

- to provide his/her dated and signed English Curriculum Vitae (CV) (maximum 2 pages) or to complete in English the CV form provided by the sponsor and to send it to the sponsor, together with that of his/her co-investigator(s),
- to provide a detailed description of the methods, techniques, and investigational equipment, and the reference values for the parameters measured,
- to provide any other document required by local regulation (e.g. Food & Drug Administration 1572 form),
- to send, a copy of the IEC's opinion with details of its composition and the qualifications of its constituent members.

The CVs of other members of the team involved in the study (if possible, in English) will be collected during the course of the study (at least, members involved in the participants' medical follow-up/study-related decision process and persons involved in the measurement of main assessment criteria).

# 19. APPENDICES

Appendix 1: ALL-MB 2015 protocol

Appendix 2: NCCN guidelines 2020

Appendix 3: Patient performance status

Appendix 4: Hepatotoxicity form

Appendix 5: Trial Conduct During National or International Public Health Emergency

Appendix 6: World Medical Association Declaration of Helsinki

Appendix 7: Instructions to investigator for handling data rights requests

| AST | : Aspartate aminotransferase |
| BMI | : Body Mass Index |
| BSA | : Body Surface Area |
| CBI | : Central Business Intelligence |
| CI | : Confidence Interval |
| Cmax | : maximum Concentration |
| CoV | : Coefficient of Variation |
| CTC | : Common Terminology Criteria |
| CTCAE | : Common Terminology Criteria for Adverse Events |
| DAP | : Data Analysis Plan |
| ECG | : ElectroCardioGram |
| FAS | : Full Analysis Set |
| GMR | : Geometric Mean Ratio |
| IAS | : Immunogenicity Analysis Set |
| IMP | : Investigational Medicinal Product: a pharmaceutical form of an active ingredient or placebo being tested or used as a reference in a clinical trial (test drug / placebo / reference product) |
| I.R.I.S. | : Institut de Recherches Internationales Servier |
| IRS | : Interactive Response System |
| MedDRA | : Medical Dictionary for Regulatory Activities |
| NCI | : National Cancer Institute |
| PAA | : Plasma Asparaginase Activity |
| PEG | : PolyEthylene Glycol |
| PK | : PharmacoKinetics |
| PKAS | : Pharmacokinetic Analysis Set |
| RDI | : Relative Dose Intensity |
| SAE | : Serious Adverse Event |
| SAP | : Statistical Analysis Plan |
| SAS | : Safety Analysis Set |
| SD | : Standard Deviation |
| TEAE | : Treatment Emergent Adverse Event |
| TLG | : Tables, Listings and Graphs |
| %CV | : Coefficient of Variation in percent |

1. INTRODUCTION

This Statistical Analysis Plan (SAP) details the planned analyses to be performed, in accordance with the main characteristics of the study protocol v2.0, dated on December 2nd, 2020, and the non substantial Protocol Amendment, dated on Apr 7th, 2021. The templates for Tables, Listings and Graphs (TLG) are described in a separate document.

1.1. Study objectives

1.1.1. Primary objective

To compare the pharmacokinetics (PK) of both lyophilized and liquid S95014 formulations during the induction phase after a single IV dose in newly diagnosed paediatric patients with ALL

1.1.2. Secondary objectives

- To describe the PK of S95014 after administration of either lyophilized or liquid formulation
- To evaluate the occurrence of treatment emergent adverse events (TEAEs) including serious adverse events (SAEs), regardless of causality and severity, based on National Cancer Institute (NCI) Common Terminology Criteria for Adverse Events (CTCAE) 5.0
- To evaluate the achievement of plasma asparaginase activity (PAA) of ≥ 0.1 U/mL after the administration of either lyophilized or liquid S95014
- To assess the immunogenicity of both lyophilized and liquid S95014 formulations

1.2. Study design

This is a multicentre, national, randomized, open-label, phase II clinical study comparing the pharmacokinetics of lyophilized and liquid Pegasparagase (Oncaspar®, S95014) formulations in the treatment of newly diagnosed, untreated pediatric patients with ALL.

1.2.1. Study plan

Each patient will be randomly assigned (1:1) to either lyophilized (arm 1) or liquid (arm 2) S95014 intravenously at the dose of 2500 U/m² at Day 3, in combination with other backbone chemotherapy agents as per local practice.

The study duration will be approximately 1.5 month, including the screening (14 days) and the treatment period consisting of the induction phase (approximately 30 days). After completing the induction phase, patient will be discontinued from the study and, provided that the inclusion/non-inclusion criteria are fulfilled, will be proposed to enter into a roll-over study (CL2-95014-003) for the consolidation phase.

[figure not shown]
The study will be divided into the following periods for each participant:

- **Screening visit (up to 14 days prior to inclusion):** to obtain informed consent and check the screening/non-screening criteria.
- **Screening period (Day -14 to Day -1):** to check the eligibility of the patient to be included in the study within 14 days prior to the inclusion.
- **Inclusion visit (Day 0):** to check inclusion/non-inclusion criteria and to confirm inclusion of the patient in the study

- **Randomization (Day 0):** the day of inclusion visit (i.e. Day 0), included subjects will be randomly assigned to one of the two treatment groups:
 - Lyophilized S95014 (arm 1)
 - Liquid S95014 (arm 2)
- **Infusion (Day 3):** the day of S95014 infusion, based on randomized treatment group.
- **Treatment period:** treatment period will start from the day of S95014 infusion, corresponding to Day 3 of the induction phase, until the withdrawal/end-of-study visit.
- **Withdrawal/End-of-study visit:** at least 30 days after S95014 infusion (i.e. Day 33) and before starting the consolidation phase. During the withdrawal/end-of-study visit, subjects will be proposed to participate in a roll-over study (CL2-95014-003) for the consolidation phase using lyophilized S95014 in combination with backbone regimen as per ALL-MB 2015 protocol.

The study plan is shown in Figure (1.2.1) 1.

Figure (1.2.1) 1 - Study plan

1.2.2. Type of randomisation

The treatment groups will be allocated via IRS using a central randomization (1:1) to either lyophilized S95014 (arm 1) or liquid S95014 (arm 2) of the induction phase.

1.3. Determination of sample size

This study is a two-arm parallel 1:1 randomized trial to evaluate the PK comparability between liquid and lyophilized S95014 formulations. For both AUC and C_{max} , the coefficient of variation (CoV) of 0.30 is assumed based on the estimation of CoV for liquid S95014 from a previous study (Angiolillo, 2014). It is also reasonable to assume a geometric mean ratio (GMR) of 100% for C_{max} and AUC, since no impact of an absorption phase is expected because both formulations are delivered intravenously. In addition, the CMC investigations have shown that once the lyophilised formulation is reconstituted, the characteristics of the solution are comparable to the ones of the liquid formulation. Assuming a CoV of 0.30 and a true GMR of 100%, a total of 78 evaluable subjects (39 subjects per arm) will provide approximately 90% power to establish the PK comparability. Assuming that 10% of the included subjects could not

be evaluable (e.g. missing PK timepoint etc.), 88 subjects are expected to be included to allow 78 evaluable subjects.

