### Determination of sample size:

This study is a two-arm parallel 1:1 randomized trial to evaluate the PK comparability between liquid and lyophilized S95014 formulations. For both AUC and  $C_{max}$ , the coefficient of variation (CoV) of 0.30 is assumed based on the estimation of CoV for liquid S95014 from a previous study (Angiolillo, 2014). Assuming a CoV of 0.30 and a true geometric mean ratio (GMR) of 100%, a total of 78 evaluable subjects (39 subjects per arm) will provide approximately 90% power to establish the PK comparability. Assuming that 10% of the included patients will not be evaluable (e.g. missing PK timepoint etc.), 88 subjects are expected to be included to allow 78 evaluable patients.

Data Monitoring Committee: Not applicable

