Bioequivalence tests will be used to compare the primary endpoints (AUC and C_{max}) in lyophilized formulation versus liquid formulation using the PKAS. Individual values of C_{max} , $AUC_{0-T_{last}}$ and AUC_{inf} will be logarithmically transformed prior to statistical analysis. An additional comparison will also be performed on $C_{day\ 14}$ for information purpose. To be specific, an analysis of variance (ANOVA) will be performed for the natural logarithms of PK parameters ($AUC_{0-T_{last}}$, AUC_{inf} , C_{max} and $C_{day\ 14}$). The ANOVA model will include fixed effect for formulation. The two one-sided tests procedure will be performed on the geometric mean ratio (GMR) between test (lyophilized pegaspargase) and reference (liquid pegaspargase) treatments. This will be done via a 90% confidence interval for the ratio obtained in the framework of the ANOVA for the logarithms. The confidence interval will be obtained by exponentiation of the upper and lower 90% confidence limits for the difference of logarithm means. PK comparability between the test treatment and the reference treatment will be concluded if the 90% confidence interval for AUC and C_{max} GMR is within the [80.00%; 125.00%] range.

Exploratory analysis may be performed to evaluate potential covariates impacting the PK parameters.

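### The stated 90% power is for one PK metric; the verdict needs both AUC and Cmax to pass, for which 78 evaluable patients give about 82–88%

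*SAP*

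**What the plan says.** The power claim appears three times: in the protocol synopsis ("approximately 90% power to establish the PK comparability"), in protocol 10.1.1 and in SAP 1.3. The SAP text reads: "a total of 78 evaluable subjects (39 subjects per arm) will provide approximately 90% power to establish the PK comparability". One CV serves AUC and Cmax alike: "the coefficient of variation (CoV) of 0.30 is assumed based on the estimation of CoV for liquid S95014 from a previous study". The true GMR is taken as 100% for both. None of the three places says that the 90% is per metric, states a correlation between AUC and Cmax, or mentions joint power.

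The decision rule is in SAP 3.5: comparability "will be concluded if the 90% confidence interval for AUC and C_{max} GMR is within the" range of 80.00% to 125.00%. Protocol 10.2.1 has the same rule, and SAP 3.5 names AUC and Cmax as the primary endpoints.

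The protocol speaks only of AUC. SAP 3.5 splits it in two and analyses both, alongside Cmax: "AUC_{0-T_{last}}$ and AUC_{inf} will be logarithmically transformed prior to statistical analysis". The decision sentence in the same section still says AUC without stating which one.

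**The concern.** The sample-size sections attach the 90% to establishing PK comparability. The analysis sections define that conclusion as two intervals both falling inside the limits. The chance of two passes is lower than the chance of one unless the two metrics always pass or fail together. If the 90% was computed for a single metric, the trial's chance of success is overstated, and so is its protection against failing two formulations that are truly the same.

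The unnamed AUC makes this worse, because the event being powered is not fully defined. If both AUCs must pass, power falls further. If either may count, there is a choice to be made after the data are seen, in an open-label trial, and the AUC test no longer holds its 5% level.

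**Working it through.** **Inputs.** CV 0.30 for both metrics, GMR 1.00 and 39 per arm (SAP 1.3). Two one-sided 5% tests through a 90% interval, limits 0.80 and 1.25, ANOVA on logs with formulation only, so df = 78 − 2 = 76 (SAP 3.5).

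**Step 1: reproduce the plan's figure for one metric.**

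- Log-scale SD: σ = √ln(1 + 0.30²) = √ln 1.09 = 0.2936.
- Standard error of the log difference: 0.2936 × √(2/39) = 0.0665.
- Limits on the log scale: ±ln 1.25 = ±0.2231.
- Normal approximation: 2Φ(0.2231/0.0665 − 1.645) − 1 = 91.3%.
- Exact power, averaging over X ~ χ² with 76 df: E[max(0, 2Φ((0.2231 − t·SE·√(X/76))/SE) − 1)], with t the 95th percentile of the t distribution on 76 df. Result: **90.7%**.
- If 0.30 is used directly as the log-scale SD, the result is 89.3%.

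All three round to about 90%, so the stated figure is power for one metric.

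**Step 2: power for AUC and Cmax together.** With no correlation, the two tests are independent and joint power is 0.9074² = 82.3%. For other correlations ρ (log scale, within arm), joint power was simulated with bivariate normal mean differences and a Wishart residual covariance, 400,000 runs per case:

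| ρ (assumed) | both pass | at least one fails |
|---|---|---|
| 0 | 82.3% | 17.7% |
| 0.5 | 83.7% | 16.3% |
| 0.7 | 85.0% | 15.0% |
| 0.8 | 86.0% | 14.0% |
| 0.9 | 87.3% | 12.7% |
| 0.95 | 88.3% | 11.7% |
| 1 | 90.7% | 9.3% |

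**Step 3: what 90% joint power would need.** At ρ = 0, 46 per arm: 92 evaluable, and 92/0.9 = 102.2, so 103 included. At ρ = 0.9, 42 per arm: 84 evaluable, and 84/0.9 = 93.3, so 94 included. The plan has 78 evaluable and 88 included.

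**Step 4: the two AUCs.** The correlation between AUC to last observation and AUC to infinity is also an assumption.

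- *Cmax and both AUCs must pass* (AUC–AUC correlation 0.97): power is about 81% at a Cmax–AUC correlation of 0 and 86% at 0.9.
- *Either AUC may count*: at a true AUC ratio of 0.80, the chance of passing on AUC rises from 5.0% to 5.8% (AUC–AUC correlation 0.98) or 6.9% (0.90). This concerns the AUC test alone. For the full verdict, Cmax must also pass. With Cmax–AUC correlations of 0 to 0.8, the false-pass probability is then 0.3–3.0% if the Cmax ratio is also 0.80, about 3–7% if it is 0.90, and about 3–6% if it is 1.00.

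**The case against.** The strongest reply is that nothing was miscalculated. The plan sets one CV and one GMR, 90% follows, and sizing per metric is common and legitimate; only a label is missing. AUC and Cmax come from the same activity profile after the same infusion, so a correlation near zero is unlikely. At 0.9 the shortfall against a figure described as approximate is about 3 points, and from about 0.94 upward it is within 2 points. Requiring both metrics is an intersection–union test, so it does not inflate type I error; the extra risk is a false failure, which falls on the sponsor.

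On the AUCs, SAP 3.5 marks only the Day 14 level as informative. The natural reading is then that all three primary intervals must pass, which is the stricter rule. Parameter details are left to a separate data analysis plan that is not available here.

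Much of this stands. The number is correct for one metric, the size of the gap depends on an unknown correlation, and no alpha adjustment is needed for requiring AUC and Cmax. Choosing between AUCs would push the false-pass probability of the whole verdict above 5% in only some configurations, and by less than 2 points.

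It does not remove the point. The sentence claims power for the joint conclusion, and that claim holds only under a near-perfect correlation that the documents neither state nor support. How the parameters are derived can be left to another document, but the decision sentence is in the SAP and does not settle which AUC counts.

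**Conclusion.** The concern holds. The 90% is the power for one metric (90.7% exact). For the conclusion it is attached to, 78 evaluable patients give about 82–88% over assumed correlations of 0 to 0.95, with 90.7% as the ceiling at perfect correlation. The risk of failing two truly identical formulations is therefore about 12–18% over that range. These figures rest on the plan's own CV of 0.30 and GMR of 100%.

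The undefined AUC is a secondary but real gap. On the stricter reading, power falls to about 81–86%; on the looser one, the AUC test runs at 5.8–6.9% instead of 5%. The power shortfall leaves the type I error of the AUC-and-Cmax rule intact and does not invalidate the analysis. It should be corrected because the trial's stated chance of success is not the one its decision rule delivers.

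**What to change.** In the synopsis, protocol 10.1.1 and SAP 1.3, state that 78 evaluable patients give about 91% power for each of AUC and Cmax separately, and about 82–88% for both together, depending on their correlation. If an AUC–Cmax correlation can be supported from earlier data, cite it and give the single joint figure.

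In SAP 3.5, add one sentence before database lock that names the AUC entering the decision rule and calls the other supportive. AUC to infinity is one candidate, since protocol 2.2.2 cites its earlier value, but what matters is that the choice is fixed in advance. If the sponsor intends both AUCs to be decisive, say so and quote the lower power.

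The cost is a change of wording in three places and one added sentence, with no more patients. The stated power becomes somewhat less favourable. Sizing for 90% joint power instead would take 84–92 evaluable patients (94–103 included) for correlations from 0.9 down to 0. That is optional, provided the power is labelled correctly.
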